3.1.5. Response Evaluable Analysis Set

The response evaluable analysis set will include all patients who are in the efficacy analysis set and have a baseline tumor assessment, and either (i) have at least 1 post-dose evaluable tumor assessment, or (ii) do not have post-dose tumor assessment, but have clinical progression as noted by the investigator or have died due to any cause before their second post-dose tumor assessment. The response evaluable analysis set will be used for analyses of anti-tumor response.

3.2. Protocol Deviation

Protocol deviations including deviations are recorded as outlined in the latest version of the Protocol Deviation and Non-compliance Management Plan. All major and minor protocol deviations will be reviewed and confirmed prior to final database lock.

4. ENDPOINTS

4.1. General Principles for Derived and Transformed Data

4.1.1. Reference Start Date and End Date and Study Day

(1) Reference start date

Dose escalation part:

For efficacy analysis, reference start date (Day 1) is defined as the first date when a non-zero dose of study treatment in continuous dosing cycle (i.e. excluding single oral dose from the PK week) is administrated.

For safety analysis, reference start date (Day 1) is defined as the first date when a non-zero dose of study treatment (i.e. including single oral dose from the PK week) is administrated.

Dose expansion part:

Reference start date (Day 1) is defined as the first date when a non-zero dose of study treatment is administrated.

(2) Reference end date

Reference end date is defined as the last date when a non-zero dose of study treatment is administered.

(3) Study day

Study day will be calculated from the reference start date, and it will be used to show start/stop day of assessments or events relative to the start date of study treatment.

- If the date of the event is on or after the reference start date, study day = (date of event – reference start date) + 1.
- If the date of the event is prior to the reference start date, study day = (date of event – reference start date).

Note that, the day of the first dose of study drug is day 1 and the day before it is day – 1, not day 0.

In the situation where the event date is partial or missing, the date will appear partial or missing in the listings.

4.1.2. Last known alive date

Last known alive date will be derived for patients not known to have died at the analysis cut-off date using the latest date (including complete date and partial date with Month and Year information) among the following data:

- All assessment / scan / sample collection dates (e.g., laboratory, vital signs assessments, ECG, eastern cooperative oncology group (ECOG), physical examinations, performance status assessment, tumor assessment dates, ophthalmologic examination, etc.).
- Medication dates, including study medication, concomitant medications, anticancer therapies administered after study treatment discontinuation.
- Procedure dates, including concomitant procedures, anticancer radiotherapies / procedures taken after study treatment discontinuation, blood transfusion.
- Adverse events start and end date, date when AE became serious, hospitalization start and end date.
- Date latest contact collected on 'Survival Follow-up' or 'Efficacy Follow-up' page where subject status is 'Alive'.

4.1.3. Baseline and Change from Baseline

Baseline is defined as the last non-missing assessment on or prior to the first administration of study treatment, including scheduled and unscheduled visits, unless otherwise specified. For quantitative measurements,

- change from baseline (CFB) will be calculated as: $CFB = \text{Assessment value at visit X} - \text{Baseline value}$;
- percentage CFB (% CFB) will be calculated as $\% CFB = (\text{Assessment value at each visit X} - \text{Baseline value})/\text{Baseline value} \times 100$.

4.1.4. Treatment Period

Unless otherwise specified, the treatment period is defined as the duration from the date of the first study drug administration to 30+7 days (7-day window only replies to parameters collected by visit) after the date of last administration of study drug or prior to the start of a subsequent anti-tumor therapy (whichever comes first). For safety data, only the assessments/events collected during the treatment period will be summarized.

The worst post baseline is defined as the worst assessments/events during the treatment period including both scheduled and non-scheduled visit. Only the on-treatment safety assessments will be included in the summary tables.

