6.1.18 End of Treatment Visit

Patients who have completed the study or have discontinued study treatment will be asked to return to the investigational site to have safety examinations and assessments within 7 days (± 3 days) after the last dose of the study drug.

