6.1.19 Follow-up Period

Safety Follow-up

All patients who have completed an EOT Visit will have a Safety Follow-up Visit. The Safety Follow-up Visit will be conducted at 30 days (± 7 days) from EOT Visit.

AEs related to the study drug will be followed until resolution and SAEs will be followed until resolution regardless of the relationship to the study drug.

All female patients of childbearing potential must complete a pregnancy test (serum or urine) during the Safety Follow-up Visit. Pregnancy testing should be repeated for patients with suspected pregnancy. This is not applicable for postmenopausal female patients (defined as at least 12 months of amenorrhea without alternative medical cause), and the date of menopause should be recorded instead.

Efficacy Follow-up

Patients who discontinue the study drug due to reasons other than disease progression, death, lost to follow-up, or withdrawal of consent will remain on study for tumor assessments and will be followed every 12 weeks (± 14 days) from the EOT visit or last assessment, until disease progression, initiation of new anticancer therapy, withdrawal of consent, lost to follow-up, death, conditions are met per Section [6.2.1](#), or the end of the study, whichever comes first.

Survival Follow-up

All patients will be followed for survival status every 12 weeks (± 14 days), until death, lost to follow-up, or withdrawal of consent. Survival information can be obtained via phone and information will be documented in the source documents and relevant CRFs.

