15 APPENDICES

APPENDIX 1 PK/PD/BIOMARKER/ECG ASSESSMENTS FOR ESCALATION COHORTS

Study Day	Time Relative to Dosing	Study Drug Intake	Blood Sample for PK	Blood Sample for 2-HG	Bone Marrow Sample for 2-HG	Blood and Bone Marrow Samples for Gene Mutation Analysis	ECG
Screening				X	X	X ²	X
PK week Day 1	Predose ¹		X				X ³
	0 h	X					
	0.5 h (±2 min)		X				
	1 h (±5 min)		X				X ³
	2 h (±10 min)		X				X ³
	3 h (±10 min)		X				
	4 h (±15 min)		X				X ³
	6 h (±15 min)		X				
	8 h (±15 min)		X				
Day 2	24 h (±60 min)		X	X			
Day 3	48 h (±60 min)		X	X			
Day 4	72 h (±60 min)		X	X			
Day 5	96 h (±60 min)		X	X			
Day 6	120 h (±60 min)		X	X			
Day 7	144 h (±60 min)		X	X			
C1D1	Predose ¹		X	X			
	0h	X					
C1D8	Predose ¹		X	X			
	0 h	X					
C1D15	Predose ¹		X	X			
	0 h	X					
C1D22	Predose ¹		X	X			
	0 h	X					
C2D1	Predose ¹		X	X		X ²	X ³
	0 h	X					
	0.5 h (±2 min)		X				
	1 h (±5 min)		X				X ³
	2 h (±10 min)		X				X ³
	3 h (±10 min)		X				
	4 h (±15 min)		X				X ³
	6 h (±15 min)		X				
	8 h (±15 min)		X				
C2D2	Predose ¹		X				
	0 h	X					
C2D8	Predose ¹		X	X			

Study Day	Time Relative to Dosing	Study Drug Intake	Blood Sample for PK	Blood Sample for 2-HG	Bone Marrow Sample for 2-HG	Blood and Bone Marrow Samples for Gene Mutation Analysis	ECG
	0 h	X					
C2D15	Predose ¹		X	X			
	0 h	X					
C3D1	Predose ¹		X	X	X	X ²	X
	0 h	X					
C5D1	Predose ¹		X	X	X	X ²	X
	0 h	X					
C7D1 and every 3-cycles thereafter	Predose ¹		X	X	X	X ²	X
	0 h	X					
EOT (7 ±3 days after last dose)	Anytime			X	X	X ²	
Safety Follow-up visit (30 ±7 days after end of treatment)	Anytime						X

2-HG=2-hydroxyglutaric acid; C=cycle; D=day; ECG=electrocardiogram; EOT=end of treatment; IDH=isocitrate dehydrogenase; PD=pharmacodynamic(s); PK=pharmacokinetic(s); CCI [REDACTED]

¹ Blood sample collection should be performed within 30 minutes before the dosing on that day and approximately 24 (±60 minutes) hours after dosing on the previous day (ie, Day 1 of Cycles 1 or 2). Pre-dose bone marrow sample collection should be performed within 24 hours prior to dosing.

² Bone marrow and/or whole blood will be collected for analysis of gene mutation abundance, such as IDH1, IDH2 (R140 and R172), DNMT3A, NPM1, SRSF2, RUNX1, NRAS, KRAS, ASXL1, TP53, FLT3, PTPN11, CCI [REDACTED], etc.

³ Analysis for CCI [REDACTED] genes will be performed at baseline only.

³ To be performed in triplicate with intervals of approximately 5 minutes.

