4.4. Safety Endpoints

The safety analysis set is used to evaluate the safety variables including AEs, clinical laboratory data, vital signs, single 12-lead ECG parameters, echocardiogram (ECHO)/ multiple-gated acquisition (MUGA) parameters, physical examinations, ECOG performance status, and death. The safety data during the treatment period will be summarized, and the treatment period is defined as the duration from the date of the first study drug administration until 30+7 days (7-day window only applied to parameters collected by visit) after last dose or prior to the start of a subsequent anti-tumor therapy (whichever comes first).

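### The SAP's Day 37 cut for by-visit safety data can exclude a protocol-compliant safety follow-up visit, which may fall as late as Day 47

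*SAP*

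**What the plan says.** SAP 4.1.4 runs the treatment period from first dose to "30+7 days (7-day window only replies to parameters collected by visit) after the date of last administration of study drug", or to the start of subsequent anti-tumor therapy if that comes first. It then states: "For safety data, only the assessments/events collected during the treatment period will be summarized". It adds: "Only the on-treatment safety assessments will be included in the summary tables". It also defines the worst post-baseline value as the worst within that period. SAP 4.4 repeats the limit ("until 30+7 days (7-day window only applied to parameters collected by visit) after last dose"), and so does SAP 5.2.11.

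The protocol counts from a different point. Section 6.1.19 says "The Safety Follow-up Visit will be conducted at 30 days", with a ±7 day window, from the EOT visit. Tables 1 and 2 and Section 7.2.2.2 use the same anchor. The EOT visit in turn takes place "within 7 days (± 3 days) after the last dose of the study drug" (Section 6.1.18). Appendix 1 prints it as "EOT (7 ±3 days after last dose", and Appendix 2 gives the same window.

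SAP Section 7, which lists changes from the protocol, does not mention the different anchor.

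**The concern.** Day 37 is the upper end of a 30 ±7 day visit only if that visit is counted from the last dose. Counted from the EOT visit, as the protocol has it, the nominal follow-up visit (7 + 30) already falls on Day 37, and its window runs past the cut. Whether a compliant visit enters the summary tables then depends on scheduling alone: the same result counts on Day 37 and not on Day 38.

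ECGs and clinical laboratory abnormalities are named primary safety endpoints (protocol Table 3, SAP Table 1). In Appendices 1 and 2 the safety follow-up row carries an ECG and the EOT row does not, so in those schedules the follow-up ECG is the only one planned after treatment ends. SAP 5.2.11.5 counts potentially clinically significant ECG findings during the treatment period only. Dose cohorts may be as small as 3 patients (protocol 4.1.1), so one excluded visit can change a count in a by-dose table.

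**Working it through.** All days are counted after the last dose.

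**Inputs**
- By-visit cut: 30 + 7 days after last dose (SAP 4.1.4, 4.4, 5.2.11).
- Follow-up visit: 30 ±7 days after the EOT visit, an offset *f* of 23 to 37 days, or 15 possible values (protocol 6.1.19, Tables 1 and 2).
- EOT visit on Day *e*: Days 4–10 under the 7 ±3 window of Appendices 1 and 2. Section 6.1.18 says within 7 days, ±3, which may also admit earlier visits. Two further readings are therefore run: Days 0–10 and Days 0–7.

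**The plan's own figure.** 30 + 7 = Day 37.

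**Range of permitted visit dates.** Visit day = *e* + *f*. With EOT on Days 4–10, the earliest is 4 + 23 = 27 and the latest is 10 + 37 = 47, giving 21 distinct dates. Days 38–47 are past the cut: 10 of 21 dates (47.6%).

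**Combinations past the cut.** A visit is excluded when *e* + *f* > 37, that is, when *f* runs from 38 − *e* to 37. That is *e* of the 15 offsets: 4 of 15 with EOT on Day 4, 7 of 15 on Day 7, and 10 of 15 on Day 10. Summing over the EOT days allowed:

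| EOT days | Visit range | Excluded combinations | Share |
|---|---|---|---|
| 4–10 | Days 27–47 | 4+5+…+10 = 49 of 7 × 15 = 105 | 46.7% |
| 0–10 | Days 23–47 | 0+1+…+10 = 55 of 11 × 15 = 165 | 33.3% |
| 0–7 | Days 23–44 | 0+1+…+7 = 28 of 8 × 15 = 120 | 23.3% |
| Visit counted from last dose | Days 23–37 | 0 of 15 | 0% |

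The last row shows that the SAP's limit fits the follow-up window exactly when the anchor is the last dose. The mismatch comes from the anchor, not from the length of the window.

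**After the change.** A limit of 37 days after the EOT visit (at most 10 + 37 = Day 47 with an in-window EOT visit) leaves no permitted date excluded by the day limit. The cut at subsequent anti-tumor therapy still applies.

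**The case against.** The strongest reply is that a fixed period after last dose is a legitimate definition of on-treatment data, and one the SAP uses consistently. TEAEs, on-treatment deaths and concomitant medications are all counted from last dose. The SAP never says what the extra 7 days are for, so it is an inference that they were meant to admit the follow-up visit. That much stands. But the SAP gives the 7 days to visit-based parameters and withholds them from AEs, so it already departs from its 30-day rule for visit data. It neither says that compliant follow-up visits may be left out nor gives a reason.

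The anchor can also be argued. The appendices label the follow-up visit as 30 ±7 days after end, or termination, of treatment. If that meant last dose, nothing would be excluded. Section 6.1.19 and Tables 1 and 2 name the EOT visit explicitly, so they are the better guide.

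Three stronger readings are tempting, and the documents do not support them.
- *About half of patients lose their follow-up data.* The 47% needs the 7 ±3 EOT window and equal likelihood of dates. The documents give no distribution of actual visit dates, and patients who start new anti-tumor therapy are cut earlier in any case.
- *Any visit later than nominal is excluded.* With EOT on Day 4, a follow-up visit 33 days later, three days past its target, falls on Day 37 and is kept.
- *The data are lost.* SAP 5.2.11.4 to 5.2.11.6 list all laboratory, ECG and vital-sign data.

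A wider period has a cost too. More off-drug values could set the worst post-baseline grade, and the by-visit period would move further from the TEAE period.

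**Conclusion.** The mismatch is real and minor. By-visit safety data are cut at Day 37, while a protocol-compliant safety follow-up visit can fall as late as Day 47 (Day 44 if EOT must fall within 7 days). Between 23% and 47% of permitted EOT/follow-up combinations lie past the cut, depending on how the EOT window is read and assuming that all permitted dates are equally likely. The conclusion rests on the EOT-visit anchor in protocol 6.1.19 and Tables 1 and 2.

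The effect is on the summary tables, for this one scheduled visit per patient. AEs are outside the point: they follow the 30-day rule in SAP 4.4.2, under which treatment-related SAEs count even later. No hypothesis test is planned, so no inference is at risk. What is at risk is a complete tabulation of post-treatment ECG and laboratory findings, which belong to the primary safety endpoints.

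**What to change.** In SAP 4.1.4, 4.4 and 5.2.11, for parameters collected by visit, extend the period to include the scheduled safety follow-up visit, up to 30 + 7 days after the EOT visit. Where there is no EOT visit date, use 47 days after last dose. Keep the cut at the start of subsequent anti-tumor therapy, and leave the 30-day AE rule as it is.

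The cost is a wording change in three sections, one derivation rule and its fallback. With an in-window EOT visit, up to 47 − 37 = 10 more days of off-drug data can enter the worst post-baseline summaries. Showing the follow-up visit as its own row in the by-visit tables lets a reader see what it contributes. If the Day 37 limit is deliberate, the SAP should say so and state that compliant follow-up visits after that day appear in listings only.

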4.2. Efficacy Endpoints

4.2.1. Best Overall Response

Assessment of anti-tumor response for patients with AML will be conducted according to 2017 European Leukemia Net (ELN) criteria (Döhner et al, 2017). Best overall response (BOR) is defined as the best response during the anti-tumor evaluation period, which will be determined using time point responses (TPRs) from date of the first dose of study treatment from Cycle 1 in continuous cycle (i.e. not from the date of single oral dose from the PK week for the dose escalation part) up until the last evaluable TPR prior to or on the date of (i) disease progression (at least 2 cycles of study drug should be administered to determine PD) / relapse according to the 2017 ELN criteria, or death; or (ii) withdrawal of consent or lost to follow-up; or (iii) receiving subsequent anti-cancer therapy, whichever is earlier.

The hierarchical order of these response categories is complete response with negative minimal residual disease (CR_{MRD-}) > complete response (CR) > complete response with partial hematological recovery (CRh) > complete response with incomplete count (CRI) > morphologically leukemia-free state (MLFS) > partial response (PR) > stable disease (SD) > progressive disease (PD) > NE (not evaluable), where CR_{MRD-} , CR and CRI are based on investigator assessment of response, and CRh will be derived from relevant data including investigator-collected bone marrow and hematology data by medical team as external file, as CRh is not defined in ELN 2017. This order will be used to derive the BOR. For example, a patient who has 4 anti-tumor assessments during the anti-tumor evaluation period with response being MLFS, PR, SD, and PD respectively, then the BOR for this patient will be MLFS.

Of note, for the BOR being SD, it is expected that the duration of SD lasts for at least 3 cycles, for example, if a patient only has one tumor assessment at 2 cycles with response being SD, then, the BOR for this patient will be NE instead. For the BOR being PD, at least 2 cycles of study drug should be administered, for example, if a patient only has one tumor assessment at 1 cycle of study drug with response being PD, then, the BOR for this patient will be NE instead.

Moreover, subjects who do not have post-dose tumor assessment, but have clinical progression as noted by the investigator or have died due to any cause before their second post-dose tumor assessment, BOR will be PD.

For patients whose BOR is 'NE', reasons for NE will be summarized as followings:

- All post-baseline overall responses are NE / No baseline or post-baseline assessments;
- Initiation of subsequent anti-tumor therapy prior to the first post-baseline tumor assessment;
- SD lasts less than 3 cycles;
- Less than 2 cycles of study drug to determine PD.

